This is a phase I, open-label, single institution, non-randomized study of escalating doses of daily, orally administered lenalidomide in combination with standard doses of everolimus, an orally available mTOR inhibitor. The trial is open to patients with advanced solid malignancies who have failed or are intolerant of available standard treatment options for their disease. Dose escalation will proceed in a modified Fibonacci 3+3 fashion with the requirement that dose escalation to the next level can only proceed if 0 of 3 or ≤ 1 of 6 patients experience a dose limiting toxicity (DLT). Five escalating dose cohorts and three deescalating dose cohorts (if DLT is encountered with the starting dose) will be used to evaluate different doses of lenalidomide and everolimus starting with the approved and or clinically relevant doses of both agents. The proposed starting dose level 1 is 10mg of lenalidomide in combination with 5mg of everolimus both administered on a once daily continuous dosing schedule for 28 days respectively in a 28-day cycle. A serial de-escalation to 10mg of lenalidomide (21 of 28 days) and 5mg of everolimus every other day will be carried out if DLT is observed in $\geq 33\%$ of patients enrolled to the starting dose cohort. The MTD is the highest dose level of lenalidomide and everolimus (up to a maximum dose of 25mg and 10mg respectively) at which $<33\%$ of the dose cohort experiences DLT after 1 cycle (28 days) of therapy. The established MTD will be the recommended dose for follow-up phase II study. To obtain preliminary evidence of potential clinical benefit of this combination, an expanded cohort of 15 patients with clear cell renal cell carcinoma, adenoidcystic carcinoma and neuroendocrine tumors will be treated at the defined MTD.

A parallel expansion cohort of 9 patients with adenoidcystic cancer will be treated at the RP2D

STUDY ENDPOINTS**Primary:**

- The MTD is the maximum doses of both drugs that can be administered without inducing DLT in $\geq 33\%$ of the treated patient cohort.
- Safety will be assessed according to NCI CTCAE 4.0v
- Assessment of DLT will be performed during the first cycle only and the following will constitute DLT in this study:
 - Grade 4 hematological toxicity lasting more than 7 days
 - Grade 4 Neutropenia of any duration in the presence of fever ≥ 38.5 c
 - Grade ≥ 3 nausea and or vomiting in spite of standard supportive therapy
 - Grade ≥ 3 non-hematologic toxicity (excluding alopecia)

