5.1 Overall design

This is a phase I, open-label, single institution, non-randomized study of escalating doses of daily, orally administered lenalidomide in combination with standard doses of everolimus, an orally available mTOR inhibitor. The trial is open to patients with advanced solid malignancies who have failed or are intolerant of available standard treatment options for their disease. Dose escalation will proceed in a modified Fibonacci 3+3 fashion with the requirement that dose escalation to the next level can only proceed if 0 of 3 or ≤ 1 of 6 patients experience a dose limiting toxicity (DLT). Four escalating dose cohorts and three deescalating dose cohorts will be used to evaluate different doses of lenalidomide and everolimus starting with the approved and or clinically relevant doses of both agents. The proposed starting dose level 1 is 10mg of lenalidomide (days 1 – 28) in combination with 10mg of everolimus (days 1 - 28) in a 28-day cycle. A serial de-escalation to 10mg of lenalidomide (days 1-21 of a 28 day cycle) and 5mg of everolimus will be carried out if DLT is observed in $\geq 33\%$ of patients enrolled to the starting dose cohort. The MTD is the highest dose level of lenalidomide and everolimus (up to a maximum dose of 25mg and 10mg respectively) at which $<33\%$ of the dose cohort experiences DLT after 1 cycle (28 days) of therapy. The established MTD will be the recommended dose for follow-up phase II study. To obtain preliminary clinical benefit of this combination, an expanded cohort of 15 patients with clear cell renal cell carcinoma, adenoidcystic carcinoma and neuroendocrine tumors will be treated at the define MTD. To allow for assessment of drug-drug interaction using PK analysis, lenalidomide will be administered alone on day 1 of the first cycle followed by both agents on day 2 cycle 1. Both drugs will be started simultaneously on day 1 of all subsequent cycles.

In addition, a parallel cohort of 9 additional patients with adenoicystic cancer will be treated at the RP2D. This is to enable us to obtain further evidence in support of the efficacy of this regimen in patients with adenoicystic cancer as observed in the limited number of patients with this cancer type who were enrolled in the escalation phase of the study.

Table 1

Dose Level	Lenalidomide (day 1 to 28)	Everolimus (day 1-28)	Patient Enrolment	Remarks
-2	10mg Days 1-21	5mg every other day	3 + 3	If DLT, study will close without defining a MTD

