-1	10mg Days 1-21	5mg	3 + 3	Deescalate to level -2 if ≥ 1 of 6 patients experience DLT, otherwise declare as MTD and expand the cohort
Starting Dose 1	10mg	5mg	3 + 3	Escalate to level 2 if 0 of 3 or 1 of 6 patients experience DLT, otherwise deescalate 1 level
2	15mg	5mg	3 + 3	Escalate to level 3 if 0 of 3 or 1 of 6 patients experience DLT, otherwise deescalate 1 level
3	20mg	5mg	3 + 3	Escalate to level 4 if 0 of 3 or 1 of 6 patients experience DLT, otherwise deescalate 1 level
4	25mg	5mg	3 + 3	if ≥ 1 of 6 patients experience deescalate 1 level, otherwise declare as MTD
5	25mg	10	3 + 3	if ≥ 1 of 6 patients experience deescalate 1 level, otherwise declare as MTD
MTD	TBD	TBD	15	Expanded cohort of 15 patients restricted to patients with renal cell carcinoma, adenoicystic carcinoma and neuroendocrine tumors

5.1.1 Blood Sample Collection:

Blood samples will be collected in heparinized green top tubes (3 mls for PK samples and 7 mls for PBMC collection), red top tube (7 mls to obtain serum sample for cytokine assay). PBMC will be purified using standard Ficoll-Paque gradient centrifugation according to the instructions of the manufacturer (Amersham Pharmacia, Uppsala, Sweden). All samples must be stored away within 1 hour of collection by refrigeration at -80°C until ready for assay.

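### Table 1 rejects one DLT in six at levels -1, 4 and 5 and gives no route from level 4 to level 5, so following it can yield an MTD below the one that the protocol's <33% definition gives

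*Combined protocol and SAP*

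**What the plan says.** **MTD definition.** Section 5.1 states: "The MTD is the highest dose level of lenalidomide and everolimus (up to a maximum dose of 25mg and 10mg respectively) at which" fewer than 33% of the cohort have a DLT in the first 28-day cycle. The synopsis endpoint says the same from the other side: "The MTD is the maximum doses of both drugs that can be administered without inducing DLT in" 33% or more of the cohort. Section 5.1 adds: "The established MTD will be the recommended dose for follow-up phase II study".

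**Escalation rule in the text.** In section 5.1, "dose escalation to the next level can only proceed if 0 of 3 or" at most 1 of 6 patients have a DLT.

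**Table 1, levels 1 to 3.** These rows agree with the text. Level 3, for example: "Escalate to level 4 if 0 of 3 or 1 of 6 patients experience DLT, otherwise deescalate 1 level".

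**Table 1, levels 4 and 5.** After a greater-than-or-equal sign, both rows read: "1 of 6 patients experience deescalate 1 level, otherwise declare as MTD".

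**Table 1, level -1.** De-escalation to level -2 follows if at least "1 of 6 patients experience DLT, otherwise declare as MTD and expand the cohort".

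**Table 1, level -2.** The study closes without an MTD if there is a DLT, with no count given.

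**Which source governs.** Sections 5.6.1, 5.7.1 and 5.7.3 all send cohort decisions to Table 1. No section says what happens when the table and the MTD definition disagree.

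**Number of levels.** The synopsis has "Five escalating dose cohorts and three deescalating dose cohorts". The text of 5.1 counts four escalating cohorts. Table 1 lists five levels from the starting dose upward and two below it. Section 10.6 plans up to 30 escalation patients, or 15 if no DLTs occur.

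**The concern.** The table that steers the trial and the sentence that defines its primary endpoint treat the same result differently. One DLT in six is acceptable under the definition and a reason to step down under rows -1, 4 and 5. Row 4 ends in either de-escalation or an MTD declaration, so level 5 cannot be reached as written, although it is a listed row.

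The MTD becomes the recommended phase II dose by rule, and the 24 expansion patients (15 + 9) are to be treated at it. Section 9.1 ties the main report to the last expansion enrolment, so the dose label carries into that report. Table 1 is the stricter of the two sources, so any error is towards a dose set too low.

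**Working it through.** **1. The plan's own counts.** Section 10.6 reproduces with five levels: 5 × 6 = 30 and 5 × 3 = 15. Four levels would give 4 × 6 = 24 and 4 × 3 = 12. The sample size therefore needs level 5, as do row 5 itself, the 25/10 mg cap and the five cohorts in the synopsis.

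**2. The threshold.** 1/6 = 16.7%, which is below 33%, so the definition accepts it. 2/6 = 33.3%, which is not below 33%, so it is rejected. Rows -1, 4 and 5 step down at 1 or more of 6, so they reject both.

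**3. Results on which the two sources part** (doses are lenalidomide/everolimus in mg):

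| Result | Table 1 as written | MTD definition |
|---|---|---|
| 1/6 at level 5 | down to 25/5 | 25/10 qualifies |
| 1/6 at level 4 | down to 20/5 | 25/5 qualifies; 25/10 if level 5 is opened and clears |
| 0/3 at level 4 | MTD is 25/5 | 25/10 if level 5 is opened and clears, otherwise the same |
| 1/6 at level -1 | down to level -2 | level -1 qualifies |
| 1/6 at level -2 | study closes, if read literally | level -2 qualifies |

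They agree for no DLT at level 5 and for two or more DLTs at level 4.

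**4. Were the disputed rows used?** Section 10.6 says escalation took 21 patients, with up to 6 per level. Levels 1 to 3 hold 3 × 6 = 18. If at least 19 of the 21 were evaluable, a fourth level was needed, so row 4 or row -1 came into play. With 3 or more replacements (21 − 3 = 18) this inference fails. It says nothing about which DLT counts were seen.

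**5. Size if level 5 was opened.** The documents give no DLT rates, so the true level-5 rate p is assumed, with q = 1 − p. The disputed result is then exactly one DLT in six at level 5, given that level 5 was entered.
- If 0/3 is enough to clear, the path is one DLT in the first three and none in the next three: 3pq² × q³ = 3pq⁵. At p = 0.10, 3 × 0.10 × 0.9⁵ = 0.177.
- If six patients are always treated, as the wording "1 of 6 patients experience deescalate 1 level, otherwise declare as MTD" could imply, it is 6pq⁵, exactly double.

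| Assumed p | 0.10 | 0.15 | 0.20 | 0.30 | 0.40 |
|---|---|---|---|---|---|
| 3pq⁵ | 0.177 | 0.200 | 0.197 | 0.151 | 0.093 |
| 6pq⁵ | 0.354 | 0.399 | 0.393 | 0.303 | 0.187 |

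**The case against.** **Row 4 need not contradict the escalation rule.** The rule in 5.1 says when escalation is permitted and does not order it, so a stricter row 4 is compatible with it. This stands. The firm conflict is with the MTD definition.

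**Table 1 governs, so the team knew what to do.** Three sections do point to it. That settles cohort assignment, but it does not make the resulting dose the highest level with under 33% DLTs.

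**Row 4 is probably a leftover from a four-level plan.** This is likely, given the four cohorts still in 5.1, and level 5 may well have been opened. Larger probabilities follow only from the literal dead end. At an assumed 10% DLT rate at both levels, the chance that the final MTD differs, given entry to level 4, is 0.729 × 0.906 + 0.177 = 0.838. Of that, 0.660 comes solely from treating 0/3 at level 4 as final. That reading is the less plausible one, so such figures should not lead.

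**A reader might infer that the declared MTD is wrong, or that any disputed result would make it wrong.** The documents support neither. The available text of section 3.4 breaks off as it begins to describe escalation patients, which is not held against the plan, and no DLT counts per level can be seen. If 25/10 was declared after 1/6 at level 5, the definition is met. If level 4 cleared and level 5 was never opened, 25/5 still has under 33% DLTs, and no listing can show whether level 5 would have cleared.

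**Escalation is over, so new wording changes no assignment.** True. What remains is to check and label the dose correctly.

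**Conclusion.** The inconsistency is certain on the page and needs no assumption about DLT rates. Rows -1, 4 and 5 reject a result that the MTD definition accepts, row -2 does so if read literally, and row 4 lacks the branch to level 5 that the rest of the plan requires.

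The MTD differs between the sources in two situations: 1/6 occurred at level -1, 4 or 5 and Table 1 was followed; or level 4 cleared and level 5 was not opened but would have cleared. In both, the recommended dose is too low. This is not a finding of excess toxicity, nor that the trial's declared MTD is in error.

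If level 5 was opened, the chance of the disputed result there is about 0.09 to 0.20, or about 0.19 to 0.40 if six patients are required, over assumed DLT rates of 10 to 40%. Whether it happened is unknown. The point should be fixed because the MTD is the primary endpoint and the remedy is small.

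**What to change.** 1. In Table 1, change the de-escalation threshold in rows -1, 4 and 5 from at least 1 of 6 to at least 2 of 6.
2. Make row -2 close the study only at two or more DLTs.
3. Make row 4 escalate to level 5 after 0 of 3 or 1 of 6, and otherwise step down one level.
4. Correct the stale text: five escalating cohorts and a 5 mg starting everolimus dose in 5.1 (it now gives 10 mg, against 5 mg in Table 1, the synopsis and 5.6.2), and a number of de-escalation cohorts that matches Table 1.
5. Report patients treated, replacements and DLTs per level, state which rule was applied, and confirm the declared MTD and recommended dose under the <33% definition.
6. If Table 1 was followed literally and a level with 1/6 was rejected, or if level 5 was permitted but never opened, describe the recommended dose as the one selected under the stricter Table 1 rule, not as an established MTD.

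The cost is amendment wording and a check of the individual DLT listing that section 10.4 already requires. No patients are added: 21 + 15 + 9 = 45 already uses the whole sample.

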5.1.2 PK Analysis –

PK Analysis will not be performed in this study. This information will be obtained in a separate ongoing phase I study of this combination in patients with hematologic malignancies where everolimus and lenalidomide concentrations will be assayed in blood with a liquid chromatography/mass spectroscopy assay as previously described.^{18,19}

5.1.3 Immunohistochemistry for mTOR pathway protein –

Archival paraffin embedded tissue collected at the time of patient screening will be shipped to the lab of the PI, [name], PhD at the Winship Cancer Institute. After obtaining a separate informed consent from trial subjects, CT -guided biopsy will be performed using either fine-needle aspiration for lung metastases or a 17 gauge biopsy gun for all other organ sites. Biopsies will be directed by a specialist from the Interventional Radiology department. Accessible lesions may also be biopsied by a preferred surgeon or other specialist as appropriate for the site. Submitted material obtained by various biopsy methods will be embedded in paraffin. Archival and fresh tumor biopsies will be stored until the end of the trial when all samples will be analyzed in a single batch. Immunohistochemical detection of the mTOR pathway proteins will be carried out with the avidin-biotin technique using specific monoclonal antibodies in the laboratory of the principal investigator, [name] in collaboration with [name]. Paired fresh tumor biopsy will be limited to patients enrolled in the expansion cohort. The final decision to proceed with fresh biopsy will however, be based on the experience in the escalation phase of the study and will require express approval of celgene.

Assess for myb protein expression by IHC in patients with adenoidcystic cancer and correlate with response to therapy.

5.1.4 Flow Cytometry for Detection and Quantification of T-cell Subsets -

At the appropriate time points as specified in the treatment schema (baseline, with the first 2 restaging assessment and at disease progression), 7 mls of anticoagulated whole blood sample will be collected and sent to the lab of [name], a collaborator at the Winship Cancer Institute, who will perform flow cytometry for the detection of different subsets of circulating T and B lymphocytes.

5.1.5 ELISA Assay for Circulating Cytokine and Angiogenesis Mediators -

[figure not shown]
ELISA detection and quantification of the cytokines of interest will be performed using previously published methods. Samples will be collected at baseline, with the first 2 restaging assessment and at disease progression. Samples will be loaded onto a 96-well microtiter plate coated with monoclonal antibody specific for the cytokine of interest. After a blocking step, samples will be diluted into a buffer and incubated with the primary antibody. After a washing step, antisera specific for the cytokine is added followed by additional incubation. Another washing step will be performed to be followed by the addition of peroxidase-conjugated secondary antibody. The concentrations of the respective cytokines will be determined in triplicate for each serum samples using an ELISA plate reader. A set of calibrators and assay controls will be run with each assay. The ELISA assays will be performed by [name] lab.

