 - Inability to re-treat patient within 2 wks of scheduled treatment due to treatment-related adverse event
 - Inability to deliver all doses of Lenalidomide and or Everolimus during the first cycle due to an unexpected drug-related toxicity (if toxicity is an

expected toxicity as per current package insert, then it will not be considered a DLT). These subjects should be discontinued from the study

In the event of study discontinuation prior to completing the entire first treatment cycle for reasons other than DLT, the affected subject will be considered inevaluable for toxicity and will be replaced by another subject to be treated at the same dose-level.

Secondary:

- Significant drug-drug interaction will be determined through pharmacokinetic analysis for parent drug and metabolites (the following PK parameters will be estimated and reported for each agent according to dose level – (AUC_{0→t}) Area under the concentration-time curve from the time of dosing to the time of the last observation; (AUC_{0→∞}) Area under the concentration-time curve from the time of dosing extrapolated to infinity; (C_{max}) Maximum serum concentration observed postdose; (T_{max}) Time point at which the C_{max} occurs; (t_{1/2}) Elimination half-life, determined as 0.693/λ_z)
- The frequency of achieving a complete plus partial response to the 2 drug combination by dose cohort. Response will be assessed by cross sectional imaging after every 2 cycles and will be categorized according to RECIST 1.1 criteria.

Correlative:

- Mean change in immunological biomarkers at baseline, after 1 cycle of protocol directed therapy and at disease progression by dose cohort
- Mean change in plasma levels of inflammatory markers at baseline, after 1 completed cycle of therapy and at disease progression
- Plasma level of cathepsin G at baseline, after 1 cycle of therapy and following the first diagnosis of venous thromboembolic disease

STUDY DURATION: 18-24 months	TOTAL SAMPLE SIZE: 45

DOSING REGIMEN(S):
 
According to dose cohort:
 
Lenalidomide once daily days 1-28 of a 28 day cycle
 
Everolimus once daily continuously (day 1-28)
	
DRUG SUPPLIES:
 
For study participants, Celgene Corporation will provide lenalidomide at no charge through the RevAssist® program.
 
Everolimus will be supplied by Novartis Pharmaceuticals Corporation and dispensed through the Investigational Drug Pharmacy

2 Schedule of Study Assessments *

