4.2.3 Correlative Endpoints

- Immunoscore of mTOR pathway protein expression (S6, pS6, 4E-BP1, p-4E-BP1, eI4F, Akt, pAkt, raptor, rictor, PRAS40, mSin1, FKBP38, and IRS-1 and HIF1- α) in archival biopsy sample for all patients and in paired fresh tumor biopsy specimens in up to 15 patients treated at P2RD if a separate informed consent is obtained.
- Immunoscore of myb protein expression in archival tissue samples in patients with adenoidcystic cancer.
- Serum level of inflammatory and immunologic markers (IL-6, IL-8, IL-12, IFN- γ , TNF- α , sIL-2R- α , CD4+ and CD8+ T-cell, NK cell and Treg cells); markers of angiogenesis (circulating VEGF and soluble VEGFR) and level of the potent platelet aggregator, cathepsin G, will be performed in serial blood samples collected at baseline, at the end of cycle 1 and at the time of disease progression or first diagnosis of venous thromboembolism (in the case of cathepsin G) and correlated with lenalidomide therapy by dose cohort.

5 Investigational Plan

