10.3 Statistical Methodology

All data will be listed individually by subject. Continuous variables will be summarized using descriptive statistics: mean, standard deviation, median, and minimum and maximum values. Categorical variables will be summarized using number of subjects and proportion expressed as percentage. Baseline value for any specified variable is the last valid measurement before the administration of the study drug. Unless otherwise indicated, statistical significance will be declared if the two-sided p value is ≤ 0.05 .

The estimation of pharmacokinetic parameters will be performed using WinNonlin® Version 5.0 or higher. All statistical analyses will be performed using SAS® Version 9.13 or higher.

Changes in immunological markers between baseline and C2D1 samples will be compared for each patient and for each dose cohort. In addition, mTOR pathway protein expression in baseline diagnostic biopsy samples will be assessed by Immunohistochemistry (IHC) and correlated with response. The dynamic changes in biomarker expression before and after one cycle of treatment with the drug combination will be summarized using summary statistics mean and standard deviation. Comparisons between the two time points will be presented graphically and subjected to statistical analysis using the Pearson's correlation coefficient.

Missing Data Handling

Unresolved missing data may be imputed when the analysis integrity is affected. The conservative principle will be used for data imputation. For example, if an adverse event onset day is missing but the adverse event onset year and month can not exclude this adverse event as a TEAE, the adverse event will be flagged as a TEAE.

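### Soluble-marker change is planned as a raw mean and SD in small dose cohorts; a paired log-ratio analysis would be a cheap improvement if the markers are right-skewed and change in proportion

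*Combined protocol and SAP*

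**What the plan says.** Section 5.1.5 covers measurement only: "The concentrations of the respective cytokines will be determined in triplicate for each serum samples using an ELISA plate reader". How the readings become an endpoint is set elsewhere.

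The synopsis (section 1, correlative endpoints) defines the inflammatory-marker endpoint as "Mean change in plasma levels of inflammatory markers at baseline, after 1 completed cycle of therapy and at disease progression", and words the immunological endpoint in the same way by dose cohort. Section 4.2.3 lists the soluble markers: IL-6, IL-8, IL-12, IFN-γ, TNF-α, sIL-2R-α, circulating VEGF, soluble VEGFR and cathepsin G. It says that these assays "will be performed in serial blood samples collected at baseline, at the end of cycle 1 and at the time of disease progression".

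Section 10.3 contains the analysis:

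- On the unit of comparison: "Changes in immunological markers between baseline and C2D1 samples will be compared for each patient and for each dose cohort".
- On the summary, changes in biomarker expression over one cycle "will be summarized using summary statistics mean and standard deviation", with no transformation named.
- On the formal analysis of baseline against follow-up: "Comparisons between the two time points will be presented graphically and subjected to statistical analysis using the Pearson's correlation coefficient".
- The general rule for all continuous data is: "Continuous variables will be summarized using descriptive statistics: mean, standard deviation, median, and minimum and maximum values".
- The general default is that "statistical significance will be declared if the two-sided p value is" at most 0.05.

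Section 10.2 adds that marker levels are reported descriptively and explored graphically. Section 10.6 gives the cohort sizes: up to 6 per escalation level, 15 in the expansion cohort and 9 in the parallel adenoid cystic cohort. No section states a transformation, a variance, an effect size, a power or a paired test of change for any marker.

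**The concern.** A concentration cannot be negative. If it varies several-fold between patients and treatment moves it by a proportion, the absolute change is largest in the patient who started highest. In a cohort of 3 to 6, that patient can then supply most of the mean change and most of its SD.

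Section 4.1.3 asks for pharmacodynamic evidence of target modulation across escalating lenalidomide doses, so the small dose-cohort summaries carry that aim. On the raw scale, a fall shared by every patient can be lost in the SD, and one patient can make a dose level look different from its neighbours.

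**Working it through.** **The plan's own figure.** There is none for the markers. The only stated power, in section 10.6, concerns response rate (1 − 0.9^15 = 0.794) and has no bearing here.

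**Inputs from the documents.** Two-sided 0.05 (10.3); n up to 6, and 9 and 15 (10.6).

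**Assumed inputs (not in the documents).** Lognormal concentrations; between-patient natural-log SD s from 0.5 to 1.5; a true halving. The comparator, a paired t test on the raw difference, is also assumed, because the plan contains no paired test.

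**Step 1: an exact limiting case.** Let every patient's marker change by the same ratio r, with no noise. The change is then (r − 1) × baseline. Its mean is (r − 1) × mean baseline and its SD is |r − 1| × SD of baseline, so

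|t| = √n × mean / SD = √n / CV,

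where CV is the sample coefficient of variation of baseline. The size of the effect cancels. Significance requires CV < √n / t(0.975, n − 1):

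- n = 3: 1.732 / 4.303 = 0.40
- n = 6: 2.449 / 2.571 = 0.95
- n = 9: 3.000 / 2.306 = 1.30
- n = 15: 3.873 / 2.145 = 1.81

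In a cohort of 6 whose baseline CV exceeds 95%, a perfectly consistent halving is therefore not significant on the raw scale. On the log scale all six values are identical.

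**Step 2: power with noise, n = 6, halving.** Log-ratio power comes from the noncentral t distribution. With SD of log change 0.5, noncentrality = 0.693 / 0.5 × √6 = 3.40 on 5 df, giving 77%. Raw-difference power is simulated. Models A and B fix the SD of log change at 0.5 (A: equal noise at both visits; B: noise at follow-up only). Model C fixes the baseline/follow-up log correlation at 0.7, so the SD of log change is s × √(2 × 0.3) = 0.775s.

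| s | A: raw v log | B: raw v log | C: raw v log |
|---|---|---|---|
| 0.5 | 57–58% v 77% | 67% v 77% | 81% v 93% |
| 0.8 | 41% v 77% | 49% v 77% | 34% v 60% |
| 1.0 | 32% v 77% | 37% v 77% | 18% v 43% |
| 1.5 | 16% v 77% | 18% v 77% | 5% v 22% |

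The log ratio wins in every cell. The multiple passes 2 at s = 1.0 (77/32 = 2.4; 77/37 = 2.1; 43/18 = 2.4) and not at s = 0.8 (at most 77/41 = 1.9).

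**Step 3: other cohort sizes, halving.**

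- n = 3, model A: log power is only 28% (raw 15% at s = 0.5, 8% at s = 1.0).
- n = 9, model A: 85% v 95% at s = 0.5, 57% v 95% at s = 1.0.
- n = 15, model C: no difference at s = 0.5, 62% v about 90% at s = 1.0, 19% v 58% at s = 1.5.

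**Step 4: how often one patient dominates.** This is the share of cohorts in which one patient supplies more than half of the total absolute change. At s = 1.0 in model C it is about 81% for n = 3, 38% for n = 6 and 6% for n = 15. At s = 0.5 and n = 6 it is 6% (C) to 14% (A).

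**Step 5: the planned Pearson correlation.** Multiplying every follow-up value by r leaves Pearson's coefficient unchanged, and so does adding log r on the log scale. In simulation at n = 6 it is significant in about 38% of trials whether the true ratio is 1 or 2, and in about 37% after logging. It does not measure change on either scale.

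**The case against.** A reader might infer that switching to logs would more than double the trial's power for these markers at no cost. The documents do not support that:

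- There is no planned power to double. Section 10.2 makes marker reporting descriptive, and the only named test for the two time points is the correlation, which logging does not improve.
- Skewness and proportional change are plausible, but the documents contain no marker data. If changes are additive, the log ratio gives no useful gain (n = 6: 66% raw v 62–65% log).
- Models A and B favour the log scale. As s rises, a fixed SD of log change implies an ever higher correlation (0.67, 0.89 and 0.95 for A at s = 0.5, 1.0 and 1.5). Under model C the multiple is largest where log power is itself poor.
- Part of the gain arises because the raw t test is conservative under skew: at n = 6 and s = 1.0 its type I error is about 0.02.
- Cohorts of 9 and 15 exist, and at 15 doubling needs s near 1.5.
- A log ratio needs a rule for values below the assay limit and changes the estimand.

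All of these stand, and they limit the size of the point. A further objection stands in part: individual listings, medians, ranges and plots are planned, so an extreme value or a consistent fall would be visible. But the synopsis still names the mean change as the endpoint, and seeing an outlier does not remove its weight. The mean-and-SD sentence in 10.3 follows one on tissue staining and could be read as limited to it; the synopsis wording still covers the blood markers.

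**Conclusion.** The point holds as a cheap improvement to an exploratory analysis. The plan puts soluble-marker change on the raw scale with no transformation, and in small escalation cohorts one patient can then drive the summary if the markers are right-skewed and change proportionally. For 6 patients, a halving and SD of log change 0.5, power is roughly 57–67% raw against 77% log at between-patient log SD 0.5, and 32–37% against 77% at log SD 1.0. A doubling at n = 6 needs log SD of about 1.0 or more. Cohorts of 3 stay weak on either scale. Every power figure rests on assumed lognormal data and on a paired test that the plan does not specify. The primary and secondary endpoints are unaffected.

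**What to change.** In section 10.3 and the synopsis:

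1. Define change for each soluble marker as log2(on-treatment / baseline), using the mean of the triplicate readings.
2. Report the geometric mean ratio with a 95% CI, by dose cohort and pooled, from a paired analysis of the log ratio. Let this replace the Pearson correlation between time points as the assessment of change; changing the scale and keeping the correlation would repair nothing.
3. Prespecify a rule for values below the assay limit, for example a fixed fraction of the limit with a sensitivity check.
4. Keep the individual listings and the raw medians and ranges.
5. Reconcile the sampling times. Section 10.3 compares baseline with cycle 2 day 1, and the synopsis and 4.2.3 refer to the end of cycle 1, but Appendix D schedules the post-baseline cytokine samples for day 1 of cycles 3 and 5 and at progression.

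The cost is SAP wording: no extra patients, samples or assays. The small downsides are the detection-limit rule and an estimand that becomes a ratio instead of a difference.
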